8.1.2 DEFINITION OF SERIOUS ADVERSE EVENTS (SAE)

According to the ICH-GCP Guidelines (E6), an SAE is any untoward medical occurrence during the course of a clinical investigation that is characterized by one or more of the following:

- Results in death
- Is life threatening
- Requires inpatient hospitalization or prolongation of existing hospitalization
- Results in persistent or significant disability/incapacity
- Is a congenital anomaly/birth defect
- Is an important medical event, defined as an event that does not fit one of the other outcomes, but may jeopardize the subject and may require medical or surgical intervention (treatment) to prevent one of the other outcomes. Examples include allergic bronchospasm (a serious problem with breathing) requiring treatment in an emergency room (ER), serious blood dyscrasias (blood disorders), or seizure/convulsion that does not result in hospitalization. The development of drug dependence or drug abuse would be other examples of important medical events.

The term "life-threatening" in the definition of "serious" refers to an event in which the subject was at risk of death at the time of the event; it does not refer to an event that hypothetically might have caused death if it were more severe.

"Inpatient hospitalization" is clarified as hospitalization lasting ≥ 24 hours. Admission to the hospital or prolongation of hospitalization qualifies as an SAE only if it is the result of an AE.

All SAE information must be recorded on the SAE form approved by the Sponsor. Additional follow-up information (e.g., test results, autopsy, and discharge summary) may be requested to supplement the SAE report form and can be attached as de-identified records.

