5.6 PARTICIPANT WITHDRAWAL OR TERMINATION

5.6.1 REASONS FOR WITHDRAWAL OR TERMINATION

Because the study treatment requires only one injection, best efforts will be made to encourage subjects to attend all follow-up visits. Subjects will be informed they are free to withdraw from the study at any time and for any reason. A premature discontinuation from the study will occur when a subject who signed informed consent ceases participation in this study, regardless of circumstances, prior to completion of the defined study period. Subjects can be prematurely discontinued from the study for one of the following reasons:

- AE
- Total or partial knee replacement of the target knee
- Lost to follow-up after a minimum of 3 attempts have been made to contact the subject, including sending a registered letter
- Withdrawal by subject for reason other than lack of efficacy
- Subject non-compliance
- Physician decision for reason other than lack of efficacy
- Study terminated by Sponsor
- Site terminated by Sponsor
- Request by regulatory authority
- Lack of efficacy
- Pregnancy
- Death
- Randomized by mistake without study treatment
- Other

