8.1.1 DEFINITION OF ADVERSE EVENTS (AE)

AEs in the eCRF will be classified according to the most recent US FDA definitions and in a manner consistent with ICH-GCP guidelines. As such the following definitions will be used:

An AE is any unfavorable and unintended sign, symptom, or disease temporally associated with the use of an IP or other protocol-imposed intervention, regardless of attribution. An AE may include intercurrent illnesses or injuries that represent an exacerbation (increase in frequency, severity, or specificity) of preexisting conditions (e.g., worsening of asthma).

Whenever possible, it is preferable to record a diagnosis as the AE term rather than a series of symptoms relating to a diagnosis. Fluctuations of pre-existing conditions, including the disease under study that does not represent a clinically significant exacerbation or worsening, need not be considered AEs. In order to classify AEs and diseases, preferred terms will be assigned by the

Sponsor to the original terms entered on the eCRF, using the Medical Dictionary for Regulatory Activities (MedDRA).

In this protocol, signs and symptoms of exacerbation or worsening of target knee OA will be captured in the context of efficacy assessments and recorded on specific pages of the eCRF or electronic diary. Anticipated fluctuations or anticipated deterioration (in the opinion of the Investigator) of the underlying disease (target knee OA) will not be considered as AEs nor captured on the AE page of the eCRF.

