7.4 Safety Assessments

7.4.1 Adverse Events

An AE is any unfavorable and unintended sign, symptom, or disease temporally associated with the use of an IP or other protocol-imposed intervention, regardless of attribution. Signs and symptoms of exacerbation or worsening of target knee OA were captured in the context of efficacy assessments. Anticipated fluctuations or anticipated deterioration (in the opinion of the Investigator) of the underlying disease (target knee OA) were not considered as AEs.

Severity was assessed utilizing the CDISC AESEV, which classifies AEs as mild, moderate, or severe. For analysis, relationship will be dichotomized into Unrelated (combining Not Related and Unlikely Related) and Related (combining Possibly Related and Probably Related).

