10.1 Adverse Events

All AEs collected in this study are treatment emergent events that occur during the course of the study that are not present prior to Day 1 study medication injection, or, if present at the time of study medication injection, have worsened in severity during the course of the study. AEs will be presented in summary tables depicting the number and percent of unique subjects experiencing each AE and the number of AEs overall and within each treatment group. The following summaries will be provided:

- All AEs and all SAEs by severity and relationship to study product
- AEs by highest degree of seriousness, severity, and relationship to study drug
- AEs by MedDRA system organ class and preferred term
- AEs with incidence of greater than 2% in the active treatment group sorted by preferred term incidence
- Target-knee-related AEs and SAEs sorted by preferred term incidence
- AEs leading to study withdrawal
- SAEs in subjects diagnosed with COVID-19

Separate subject-level listings will be provided for all AEs and all SAEs.

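### The exemption for anticipated target-knee OA deterioration has no limit for serious events, so surgery on the injected knee can go unreported as an AE or SAE, and other protocol text points the opposite way

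*Protocol*

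**What the plan says.** Protocol 8.1.1 holds the exemption: "Anticipated fluctuations or anticipated deterioration (in the opinion of the Investigator) of the underlying disease (target knee OA) will not be considered as AEs", and such deterioration is "nor captured on the AE page of the eCRF". Protocol 7.1.1 carries the same text. SAP 7.4.1 repeats the rule for the analysis: anticipated changes "of the underlying disease (target knee OA) were not considered as AEs".

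Protocol 8.1.2 ties the hospitalization criterion to an AE: "Admission to the hospital or prolongation of hospitalization qualifies as an SAE only if it is the result of an AE". It adds a length condition, in that inpatient hospitalization "is clarified as hospitalization lasting ≥ 24 hours".

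Protocol 5.6.1 lists "Total or partial knee replacement of the target knee" as a discontinuation reason of its own, separate from AE. Every summary listed in SAP 10.1 is built on AEs, including the target-knee AE and SAE table and the table of "AEs leading to study withdrawal".

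Two other places lean towards reporting. Under Knee Examination, Protocol 7.1.1 requires a clinically significant knee finding made after injection to be reported as an AE, and SAP 10.4 says this was done. A separate sentence in 8.1.1 exempts fluctuations of the disease under study only when they fall short of clinically significant worsening.

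**The concern.** The exemption turns on whether the Investigator regards the deterioration as anticipated. It does not ask whether the event was serious or ended in an operation. Appendix 3 (Amendment 01) explains it by saying that knee pain is an endpoint and will be captured through the efficacy measures. That reasoning covers pain scores. It does not cover surgery, because none of the efficacy measures (daily pain NRS, WOMAC, Patient Global Assessment, NSAID/acetaminophen use) records an operation on the knee.

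The agent is described in Protocol 2.2 as acting on cartilage and progenitor cells in the treated joint, and the schedule of events has no radiograph after injection. Surgery on the injected knee is therefore one of the few structural signals the trial could show. If its classification depends on which sentence a site followed, the AE and SAE tables may not compare the arms on it reliably.

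**Working it through.** No arithmetic applies, and the plan gives no figure to reproduce. The check follows one case through the rules: a subject's injected knee is replaced during the 28 weeks, and the Investigator attributes this to anticipated OA deterioration.

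**Following the exemption**

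1. Under 7.1.1 and 8.1.1 the deterioration is not an AE and is not entered on the AE page.
2. Under 8.1.2 the admission does not result from an AE, so it fails the hospitalization criterion. A stay under 24 hours would fail it in any case.
3. The 24-hour report in 8.4.2 is triggered by an SAE, so it is not triggered here. The unanticipated-problem route in 8.1.3 also starts from an AE.
4. Events of special interest (8.4.4) and halting rules (8.5) are marked not applicable, so neither gives a second route.
5. Under 5.6.1 a withdrawal can be coded as knee replacement instead of AE.
6. With no AE recorded, the subject is absent from the tables in SAP 10.1.

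**Following the other text**

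1. The knee examination finds clinically significant worsening after injection, which the Knee Examination paragraph of 7.1.1 makes an AE.
2. The fluctuation sentence in 8.1.1 does not exempt it, because the worsening is clinically significant.
3. An admission of at least 24 hours resulting from it is then an SAE.
4. The subject appears in the SAP 10.1 AE and SAE tables. The withdrawal table is less certain: the SAP does not say whether it is built from the AE page or from the disposition reason, and a knee-replacement code could still keep the subject out.

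The same event thus has two defensible codings, and no sentence says which prevails. The protocol plans about 100 centers.

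**Where the event can still be seen**

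| Route | What it gives | Limit |
|---|---|---|
| Disposition (SAP 8.1) | Discontinuation reasons by treatment group | Only subjects who withdraw; surgery other than replacement has no code of its own |
| Procedures eCRF (Protocol 7.5; SAP 12.1) | New procedures, listed by subject | Listing only, no count by arm |
| Surgery prohibition (Protocol 7.6; SAP 4.4.3) | Notice to the Medical Monitor when a prohibited therapy is needed for safety, and a protocol deviation | Not an SAE report; subjects are not automatically discontinued |
| Deviation summaries (SAP 8.2) | All deviations listed; major ones summarized by site and category | Not stated to be by arm |

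No route in this table is an SAE report, and none is a planned by-arm count of target-knee surgery.

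**The case against.** The best reply is that the protocol already blocks the gap. Only anticipated deterioration is exempt, worsening that needs joint replacement is hard to call clinically insignificant, and the knee-examination rule would make it an AE. The sentence linking admission to an AE is described in Appendix 3 as alignment with ICH, and it restricts only the hospitalization criterion; the disability and important-medical-event criteria remain. A dedicated discontinuation code, tabulated by arm, may even be more visible than one term among many AEs.

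Much of this stands. The link between admission and AE is not a defect in itself; the problem arises when it meets an exemption with no seriousness limit. The counter-text is real, but it conflicts with the exemption and does not override it. The disposition code helps for replacements that lead to withdrawal, and not for other surgery or for subjects who stay in the study.

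A reader might infer three stronger things that the documents do not support:

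- That target-knee deterioration is never an AE. Unanticipated worsening remains reportable.
- That an excess of surgery would pass unseen through medical monitoring. Protocol 7.6 requires notification of prohibited therapies needed for safety, and the Medical Monitoring Plan is not among the documents.
- That replacement lies outside what the plan foresees. Protocol 5.6.1 names it.

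**Conclusion.** The point holds as a gap and a conflict in the reporting rules. On the current text, surgery on or replacement of the injected knee attributed to anticipated OA deterioration can go unreported as an AE or SAE and be absent from the SAP 10.1 tables. Other passages would have the same event reported. The conclusion rests on the Investigator judging the deterioration anticipated and on the site applying the exemption ahead of the knee-examination rule.

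The number of subjects affected cannot be stated. The documents give no rate for target-knee surgery and none for SAEs, so any claim that the missing events would be large beside the SAE count would depend entirely on the rates assumed. Nor do the documents show that any event was in fact left out. Instructions in the eCRF Completion Guidelines, which are not available here, might narrow the gap. The correction is worth making because it is cheap and removes a written rule that can suppress SAE reports.

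**What to change.** **Protocol.** Reconcile 7.1.1, 8.1.1 and 8.1.2 with the knee-examination rule, and SAP 7.4.1 with SAP 10.4. State that the target-knee OA exemption does not apply to an event that meets a seriousness criterion or leads to surgery on, or replacement of, the target knee. Record such an event as an AE and, if a criterion is met, report it as an SAE, whether or not the Investigator thought the deterioration anticipated.

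**SAP 10.1.** Add a count by arm of target-knee surgery and replacement, taken from the procedures eCRF and disposition data, whether or not the subject withdrew and whether or not an AE was recorded. The SAP is written in the past tense and was signed in October 2021, so new reporting text cannot change completed conduct. The count remains feasible and would show whether any such event sits outside the AE tables.

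**Cost.** A few extra reports where the protocol text can still apply, and one extra table row. No new data are collected and patient care does not change. SAP section 10 plans no formal safety tests, so the count raises no multiplicity question.

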8.1.3 DEFINITION OF UNANTICIPATED PROBLEMS (UP)

An AE observed during the conduct of a study should be considered an Unanticipated Problem (UP) involving risk to human subjects, and be reported to the IRB, only if it was unexpected, serious, and would have implications for the conduct of the study (e.g., requiring a significant, and usually safety-related, change in the protocol, such as revising inclusion/exclusion criteria or including a new monitoring requirement, informed consent, or IB). The occurrence of such an event would suggest that the research places study participants or others at a greater risk of harm.

FDA recommends that there be careful consideration of whether an AE is a UP that must be reported to IRBs. In summary, FDA believes that only the following AEs should be considered

as UPs that must be reported to the IRB:

- A single occurrence of a serious, unexpected event that is uncommon and strongly associated with drug exposure (such as angioedema, agranulocytosis, hepatic injury, or Stevens-Johnson syndrome)
- A single occurrence, or more often a small number of occurrences, of a serious, unexpected event that is not commonly associated with drug exposure, but uncommon in the study population (e.g., tendon rupture, progressive multifocal leukoencephalopathy)
- An AE that is described or addressed in the IB, protocol, or informed consent documents, but occurs at a specificity or severity that is inconsistent with prior observations
- An SAE that is described or addressed in the IB, protocol, or informed consent documents, but for which the rate of occurrence in the study represents a clinically significant increase in the expected rate of occurrence (ordinarily, reporting would only be triggered if there were a credible baseline rate for comparison)
- Any other AE or safety finding (e.g., based on animal or epidemiologic data) that would cause the sponsor to modify the IB, study protocol, or informed consent documents, or would prompt other action by the IRB to ensure the protection of human subjects

8.2 CLASSIFICATION OF AN ADVERSE EVENT

8.2.1 SEVERITY OF EVENT

The Investigator will assess AEs for severity utilizing the CDISC AESEV, which classifies AEs as mild, moderate, or severe (Table 1).

Table 1: CDISC Definitions of Adverse Event Severity

CDISC Submission Value	CDISC Definition
MILD	A type of adverse event that is usually transient and may require only minimal treatment or therapeutic intervention. The event does not generally interfere with usual activities of daily living.
MODERATE	A type of adverse event that is usually alleviated with additional specific therapeutic intervention. The event interferes with usual activities of daily living, causing discomfort but poses no significant or permanent risk of harm to the research participant.
SEVERE	A type of adverse event that interrupts usual activities of daily living, or significantly affects clinical status, or may require intensive therapeutic intervention.

8.2.2 RELATIONSHIP TO STUDY AGENT

The relationship of the study treatment to an AE will be determined by the Investigator based on the following definitions:

Not Related

The AE is not related if (1) exposure to the study medication or administration of the study injection has not occurred **or** (2) the occurrence of the AE is not reasonably related in time **or** (3)

the AE is considered related to another event, medical condition, or product not associated with the study medication or the study injection.

Unlikely Related

The AE is unlikely related if (1) the AE is unlikely related in time **or** (2) the AE is considered unlikely to be related to use of the study medication or study injection (i.e., there are no facts [evidence] or arguments to suggest a causal relationship), or the AE is considered possibly related to another event, medical condition, or product not associated with the study medication.

Possibly Related

The AE is possibly related if (1) the study medication or the study injection and AE are considered reasonably related in time **and** (2) the AE could equally be explained by causes other than exposure to the study medication or the study injection.

Probably Related

Exposure to study medication or administration of the study injection and AE are probably related if (1) the study medication or study injection and AE are considered reasonably related in time **and** (2) the study medication or study injection is more likely than other causes to be responsible for the AE **or** is the most likely cause of the AE.

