8.4.2 SERIOUS ADVERSE EVENT REPORTING

The Investigator is responsible for reporting SAEs to the Sponsor and IRB according to 21 CFR Parts 50, 56, and 312.

Using the SAE Report Form, SAEs must be reported within 24 hours of study site personnel's knowledge of the event, regardless of the Investigator assessment of the relationship of the event to study drug. The Investigator should review the SAE information and sign the SAE report, and the Investigator or designee should submit the SAE report to the Samumed Study SAE email address: [contact] or [contact].

The initial report should include, at a minimum, the following:

- Investigator name
- Subject number, sex, and age
- Details of study drug administration
- The date of the report
- A description of the SAE (including event term and serious criteria)
- Causal relationship to the study drug
- If the subject died, the report should include the cause of death as the event term (with fatal outcome) and whether or not the death was related to study drug, as well as the autopsy findings if available

Follow-up information must be detailed in a follow-up SAE report and reported to the Samumed Study SAE email address or fax number as it becomes available. The Investigator also must report all SAEs promptly to the appropriate IRB/EC as required by the institution. Sponsor contact information for questions regarding SAE reporting is provided in Table 2.

Table 2: Sponsor Contact Information for Questions on SAE Reporting

Primary Contact	Alternative Contact
[name], Medical Reviewer, Drug Safety and Pharmacovigilance	[name], Scientist, Drug Safety and Pharmacovigilance
Cellular: [contact]	Cellular: [contact]
Email: [contact]	Email: [contact]

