10. SAFETY AND TOLERABILITY ANALYSIS

The analysis of safety outcome measures will be performed on the Safety Analysis Set. No formal statistical tests are planned for safety.

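### As worded, the last limb of Unlikely Related overlaps Possibly and Probably Related, and the SAP's Related/Unrelated cut falls on that overlap

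*Protocol*

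**What the plan says.** Protocol 8.2.2 gives the causality judgement to the site: "The relationship of the study treatment to an AE will be determined by the Investigator based on the following definitions". Four categories follow. No rule covers an AE that meets two of them.

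- **Unlikely Related** has two numbered limbs joined by or: (1) an improbable time relation, and (2) a link judged unlikely, explained in brackets as the absence of evidence or arguments for it. After the bracket closes, the sentence continues: "or the AE is considered possibly related to another event, medical condition, or product not associated with the study medication".
- **Possibly Related** needs two things together: that "the study medication or the study injection and AE are considered reasonably related in time", and that "the AE could equally be explained by causes other than exposure to the study medication or the study injection".
- **Probably Related** needs reasonable timing, with the study medication or injection a likelier cause than the others or the likeliest of all.

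SAP 7.4.1 states that "relationship will be dichotomized into Unrelated (combining Not Related and Unlikely Related) and Related (combining Possibly Related and Probably Related"). SAP 10.1 uses the result in "All AEs and all SAEs by severity and relationship to study product" and in a second summary by highest seriousness, severity and relationship. Protocol 10.4.4 names relationship among the bases on which safety will be judged. SAP 10 adds: "No formal statistical tests are planned for safety".

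**The concern.** A category scale for causality works only if an AE belongs in one place, or if a rule settles ties. Here the last limb of Unlikely Related sets no timing condition and makes no comparison between the alternative cause and the study treatment. A possible alternative is enough. Possibly Related is defined by an equally good alternative, so the two definitions describe the same AE.

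An overlap between Not Related and Unlikely Related would do no harm, because the SAP pools them. This overlap lies across the pooled boundary. Two sites with the same kind of event can follow the text faithfully, and one event ends up in Related and the other in Unrelated. What is at stake is how far the related-AE and related-SAE counts, which support statements about tolerability, can be compared between sites and interpreted.

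There is a second gap in the same limb. The other three categories, and the body of limb (2), refer to the study medication or the study injection; the last limb names the medication only. Protocol 2.3.1 lists infection and local site reactions as risks of the injection itself. A reaction to the needle procedure could be read as due to something not associated with the medication, and so fall into Unrelated.

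**Working it through.** The plan gives no figure to reproduce. The check is logical: write the definitions as conditions, list the combinations, and map each to the SAP's two groups.

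**Inputs** (Protocol 8.2.2 and SAP 7.4.1): timing reasonable or not; some evidence for a link or none; alternative cause absent, possible but weaker, or equal. That gives 2 × 2 × 3 = 12 combinations. Not Related is left out because it shares a SAP group with Unlikely Related.

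**With reasonable timing (6 combinations):**

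| Evidence for link | Alternative cause | Categories met as written | SAP group |
|---|---|---|---|
| Some | None | Probably | Related |
| Some | Possible, weaker | Unlikely and Probably | Either |
| Some | Equal | Unlikely and Possibly | Either |
| None | None | Unlikely | Unrelated |
| None | Possible, weaker | Unlikely | Unrelated |
| None | Equal | Unlikely and Possibly | Either |

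**Without reasonable timing (6 combinations):** Unlikely only, hence Unrelated.

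Three of the 12 combinations straddle the cut. This counts logical cases and is not a frequency. The sixth row is nearly self-contradictory, since an equally good alternative implies some case for the study treatment. Wherever Possibly appears, Unlikely appears too: on the literal wording, every AE that meets Possibly Related also meets Unlikely Related.

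**Direction of the effect.** Let p1 and p0 be the proportions with a Related AE under a consistent rule in the active and placebo arms, and let q be the share of those recorded as Unlikely, equal in both arms.

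- Reported difference = (1 − q)(p1 − p0)
- Reported ratio = (1 − q)p1 / ((1 − q)p0) = p1/p0, for q below 1

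As an assumption only, take p1 = 6% and p0 = 3%. At q = 0 the difference is 3.0 points. At q = 0.5 the rates are 3% and 1.5%, a difference of 1.5 points. At q = 1 it is 0. The ratio stays at 2 for any q below 1. Neither the rates nor q can be taken from the documents.

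**Check of remedies.** Deleting the limb resolves the second row to Probably and the third to Possibly. It also opens a gap: an AE with reasonable timing, some argument for the study treatment, and a likelier but unestablished alternative is not Possibly (the causes are not equal), not Probably, and not clearly Unlikely under limb (2). Rewording the limb to require a likelier alternative resolves the same two rows and gives that AE a category. The sixth row remains under either change.

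**The case against.** The best defence is that the four terms form an obvious graded scale. Protocol 8.2.2 numbers only two limbs under Unlikely Related, and the disputed words are an unnumbered tail of the second, so they may merely elaborate a link judged unlikely. Many investigators may read it so. That makes the overlap a matter of literal reading, and it should be described as such. It does not remove the ambiguity: the bracket has closed, a new or clause begins, nothing ties it to the preceding words, and about 100 sites (Protocol 4.1) apply the text.

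Three stronger readings are tempting, and the documents do not support them.

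- **That nearly every local knee event can be lost to Unrelated because OA is always an alternative.** Under Protocol 7.1.1 and 8.1.1 and SAP 7.4.1, fluctuation or deterioration of target knee OA that the Investigator regards as anticipated is not an AE at all. Only other knee events reach the causality step.
- **That expedited reporting is compromised.** Protocol 8.4.2 requires sites to report SAEs to the sponsor within 24 hours "regardless of the Investigator assessment of the relationship of the event to study drug". Protocol 8.4.1 and 8.2.3 give onward reporting and expectedness to the sponsor, and nothing binds the sponsor to the Investigator's category or to the SAP's grouping.
- **That the related-AE comparison is biased by a known amount, or towards one arm.** Protocol 6.1.5 and 10.6.1 keep assessment with blinded staff, so misclassification should be similar between arms. In that case the absolute difference shrinks but the ratio does not.

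It is also fair to say that SAP 10.1 plans tables by preferred term, a table of target-knee AEs, and full listings, none of which depends on the split. Local events stay visible by arm. Those tables do not repair the Related counts, and no four-category summary by arm is specified.

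**Conclusion.** The overlap stands on the literal text, it has no tie-break, and the SAP places its cut there. The consequence is limited to the descriptive related-AE and related-SAE summaries. No efficacy test, error rate or power calculation depends on it, and neither do site SAE reporting or the preferred-term and target-knee tables.

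The size cannot be stated, because the documents give neither AE rates nor the share of AEs with a plausible alternative cause. The expectation of similar misclassification in both arms rests on effective blinding and on a similar mix of event types; if the mix differed by arm, q could differ too. The point is worth acting on because the analysis part of the remedy is cheap and uses data already collected.

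**What to change.** 1. **SAP 7.4.1 and 10.1.** Tabulate AEs and SAEs by all four relationship categories, by arm. Add one sensitivity summary that counts every category except Not Related as related. Beside the planned table, this shows how far the Related count could rise if AEs recorded as Unlikely had been assigned the other way. It does not reach AEs that a site recorded as Not Related.

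2. **Protocol 8.2.2, for AEs still to be assessed or later use of the text.** Reword the limb, rather than delete it, so that Unlikely Related requires another event, condition or product to be a more likely cause than the study medication or the study injection. Equal plausibility then belongs to Possibly Related only, and the missing reference to the injection is restored.

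The cost is one extra table and one clause. The stated number of related AEs may rise in both arms. The SAP is written largely in the past tense and was signed in October 2021, and new wording does not change AEs already classified. For those, only the first step helps.
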